- Estimates of the adjusted responder rate for each treatment group and the associated SE are obtained from the logistic regression of each of the 100 imputed data sets. These estimates will be combined for overall inference using Rubin’s rules, which account for the uncertainty associated with the imputed values (Rubin, 1987), and the combined estimates and SEs will be used to construct 95% CIs using the logit scale. This will be done using SAS PROC MIANALYZE. The combined estimates and 95% CIs on the logit scale will be back-transformed using the inverse logit link function to obtain the adjusted responder rates (%) and associated 95% CIs.

Note: The (unadjusted) proportion of responders will be calculated at each time point by treatment group from the imputed datasets using SAS PROC FREQ. These results will also be combined into an overall inference using SAS PROC MIANALYZE.

Some key points to consider relative to the calculation of the odds ratios and corresponding confidence intervals are noted below:

As the estimates of the odds ratios from the logistic regression models in Step 3 follow a log-normal distribution, a log transformation is needed to normalize these 100 odds ratio estimates. That is because the procedures for combining results from multiple imputed datasets assume that the statistics estimated from each imputed dataset are normally distributed. Therefore, the log of the odds ratio estimates from the logistic regression model are used when combining into a single inference (Step 3). Additionally, the SE for the odds ratios are transformed as follows:

$$SE = \frac{\log(UCL) - \log(LCL)}{2Z_{\alpha/2}}$$

Where UCL and LCL are the upper and lower confidence limit, respectively, for the CI of the odds ratio from the logistic regression model, and $Z_{\alpha/2}$ is the relevant critical value from the standard normal distribution (2.24 for a 97.5% CI). The estimates of the log odds ratio for Bimekizumab relative to placebo and the corresponding upper and lower CLs will be provided. The odds ratio will be then estimated by exponentiating the estimate of the log odds ratio. The odds ratio and the confidence limits of the odds ratio will be estimated as follows:

$$OR = \exp(\text{Log odds ratio estimate})$$

$$LCL = OR * \exp(-SE * Z_{\alpha/2})$$

$$UCL = OR * \exp(SE * Z_{\alpha/2})$$

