Where OR is the back-transformed estimate of the odds ratio just described, SE is the SE of the log odds ratio and $Z_{\alpha/2}$ is the relevant critical value from the standard normal distribution (2.24 for a 97.5% CI). These calculations will be done such that odds ratios and corresponding CIs are calculated for the odds ratio of bimekizumab vs. placebo.

Note: If one dose regimen is tested at the 0.05 significance level as determined in Section 4.5, then the confidence interval will be 95% instead of 97.5% for that dose with a corresponding $Z_{\alpha/2}$ of 1.96.

In addition to calculating the odds ratio, associated CIs, and p-values for the pairwise comparisons of bimekizumab and placebo, the estimated proportion of responders (ie, estimated responder rate) and the difference in the proportion of responders between each bimekizumab treatment group and placebo will be estimated, and 2-sided 95% CIs will be created for each difference. The creation of the estimates of the differences will be completed for each bimekizumab treatment group using the process detailed below:

1. Use the logistic regression model to calculate:

Least squares mean estimates of the log odds of bimekizumab (G_B) and placebo (G_P), as well as their corresponding standard errors (S_B and S_P , respectively).

Standard error of the least squares mean estimate of the log odds ratio (S_R)

2. Compute estimates for predicted proportions using the following transformations:

$$P_B = \exp(G_B)/(1 + \exp(G_B))$$

$$P_P = \exp(G_P)/(1 + \exp(G_P))$$

The difference in proportions is then given by:

$$D = P_B - P_P$$

3. Estimate the standard error of D by:

$$S_D = \text{sqrt}[P_B^2(1-P_B)^2S_B^2 + P_P^2(1-P_P)^2S_P^2 + P_B(1-P_B)P_P(1-P_P)S_R^2 - P_B(1-P_B)P_P(1-P_P)(S_B^2 + S_P^2)]$$

The MCMC method for multiple imputation, as previously outlined, will be used to account for missing values. The calculation steps described above will be based on the results provided from the logistic regression model of the multiple imputed datasets. An estimate for the difference in proportions, D, and corresponding standard error, SD, will be computed for each of these datasets. The results from these analyses will be combined into a single estimate of the difference in predicted proportion of response and a 2-sided 95% CI interval using SAS PROC MIANALYZE.

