8.2.2 Primary analysis of the primary efficacy endpoint

The primary endpoint is the HiSCR₅₀ response at Week 16 and corresponding analyses are based on the RS. The primary efficacy analysis will evaluate the composite estimand in the RS as described in Table 8–1. The composite estimand combines the clinically meaningful improvement from Baseline based on the HiSCR₅₀ response and completion of study treatment through Week 16 without receiving systemic antibiotic rescue medication or discontinuing IMP due to an AE or lack of efficacy.

The following 4 attributes describe the estimand that will be used to define the treatment effect of interest for the primary efficacy analysis:

1. Population=Study participants meeting the protocol-specified inclusion/exclusion criteria.
2. Study participant-level outcome=HiSCR₅₀ at Week 16.
3. Intercurrent event handling=An intercurrent event is defined as receipt of systemic antibiotic rescue medication or discontinuation of study treatment due to an AE or lack of efficacy prior to Week 16. More information is provided in Section 3.9. A composite strategy will be implemented in which a positive clinical outcome is defined as achieving HiSCR₅₀ at Week 16 and not receiving systemic antibiotic rescue medication, and not discontinuing study treatment due to an AE or lack of efficacy through Week 16. Any missing data at Week 16 that are not preceded by an intercurrent event will be imputed using multiple imputation as defined in Section 4.2.1. The rationale for this composite estimand is provided in Section 4.2.3.1.

4. Population-level summary measure=conditional odds ratio comparing bimekizumab to placebo adjusted for stratification factors used in the randomization.

The statistical hypothesis for the HiSCR₅₀ response at Week 16 is that the conditional odds ratio for the HiSCR₅₀ response in the bimekizumab treatment group relative to the placebo group is equal to 1.

The primary analysis will be based on a logistic regression model including a fixed effect for treatment, Hurley stage at Baseline, and Baseline antibiotic use. The odds ratio versus placebo, p-value (from Wald test), and 97.5% CI will be calculated. If one dose regimen is tested at the 0.05 significance level as determined in Section 4.5, then the confidence interval will be 95% instead of 97.5% for that dose with a corresponding $Z_{\alpha/2}$ of 1.96.

The number and percentage of participants who are HiSCR₅₀ responders at Week 16 will be summarized.

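### Adjusted responder rates and their difference are inverse logits of least squares mean log odds with no weights stated, so they need not equal mean response rates in the Randomized Set

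*SAP*

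**What the plan says.** The primary model in SAP section 8.2.2 is a "logistic regression model including a fixed effect for treatment, Hurley stage at Baseline, and Baseline antibiotic use". Section 4.2.2.1 then derives two sets of absolute figures from it.

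- **Adjusted rates.** "Estimates of the adjusted responder rate for each treatment group and the associated SE are obtained from the logistic regression" in each imputed data set. They are pooled with Rubin's rules, and "The combined estimates and 95% CIs on the logit scale will be back-transformed using the inverse logit link function".
- **Difference D.** Under the instruction "Use the logistic regression model to calculate", the first item is "Least squares mean estimates of the log odds of bimekizumab (G_B) and placebo (G_P"), with their standard errors. Then P = exp(G)/(1 + exp(G)) per arm and D = P_B − P_P. The section introduces these as "the estimated proportion of responders (ie, estimated responder rate) and the difference in the proportion of responders between each bimekizumab treatment group and placebo".

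Section 4.2.2.1 also provides a crude figure per arm: "The (unadjusted) proportion of responders will be calculated at each time point by treatment group from the imputed datasets using SAS PROC FREQ". It gives no crude counterpart for the overall difference. Nowhere does the SAP say whether the least squares means use equal weights or observed margins. The current text gives no stratum shares; a 30% cap on antibiotic users appears only as deleted text in the log for Amendment 1.

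**The concern.** There are two separate difficulties.

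1. **The scale of averaging.** The inverse logit is not linear, so the inverse logit of an average log odds differs from the average of the response probabilities whenever the averaged factors affect response. This follows from the printed formulas and holds for any choice of weights.
2. **The weights.** Least squares means average over the levels of the classification effects. With nothing stated, the usual default is equal weights, which puts antibiotic users at 50% and Hurley II and III at 50% each, whatever was enrolled. The skin pain response model (section 8.3.5.1) adds analgesic use as a third such factor.

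The population attribute in section 8.2.2 reads "Population=Study participants meeting the protocol-specified inclusion/exclusion criteria", and the analysis is on the Randomized Set. A reader will take the adjusted rates and D as average response in those participants. If antibiotic users are a small minority and the factor is prognostic, the figures can differ from that average by several points. The adjusted rate would then also differ from the crude rate for the same arm, and the plan gives no explanation for the gap.

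**Working it through.** **Inputs from SAP Table 2-1.** HiSCR50: 0.60 (bimekizumab, N=280), 0.50 (bimekizumab, N=140), 0.25 (placebo, N=70). HiSCR75: 0.45 (N=280) and 0.10 (placebo).

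**Assumed, because the SAP gives no values.** Hurley III share 45% with odds ratio 0.6; antibiotic users 5-30% with odds ratio 0.5-2.

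**The plan's own figure.** HiSCR50, 0.50 v 0.25, 140 v 70, two-sided 0.025: a two-proportion calculation gives power 0.907 against the stated 0.90 (Fisher exact 0.897). It reproduces; no stated figure is in dispute.

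**Method.** For each arm, solve the intercept b so that the response probability, averaged over the four strata at their assumed shares, equals the Table 2-1 rate. Then compute:

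- equal weights: P = expit(b + 0.5·log OR_H + 0.5·log OR_A)
- observed margins: P = expit(b + s_H·log OR_H + s_A·log OR_A), where s_H and s_A are the shares
- averaged predictions: the Table 2-1 rate, by construction.

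**One case in full.** HiSCR75, 10% users, OR_A = 0.5. Log 0.6 = −0.511 and log 0.5 = −0.693, so half their sum is −0.602.

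- Bimekizumab: b = 0.091. The stratum probabilities 0.523, 0.397, 0.354 and 0.247, weighted 0.495, 0.405, 0.055 and 0.045, average to 0.450. Equal weights: expit(0.091 − 0.602) = 0.375.
- Placebo: b = −1.939, averaging to 0.100. Equal weights: expit(−1.939 − 0.602) = 0.073.
- D = 0.375 − 0.073 = 0.302, against 0.350.
- Observed margins add 0.45 × (−0.511) + 0.10 × (−0.693) = −0.299, giving 0.448 − 0.096 = 0.352.
- The conditional odds ratio is exp(0.091 + 1.939) = 7.6 under either weighting.

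**Across the assumptions** (percentages; equal weights unless marked):

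| Endpoint, enrolled rates | Antibiotic share and OR | Bimekizumab | Placebo | D | D, observed margins |
|---|---|---|---|---|---|
| HiSCR50, 60 v 25 (35.0) | 5-30%, 0.5-2 | 51.9-66.8 | 18.9-30.3 | 33.0-36.8 | 35.4-36.2 |
| HiSCR50 | 10%, 0.8-1.25 | 57.4-61.7 | 22.6-25.9 | 34.8-35.8 | 35.5 |
| HiSCR75, 45 v 10 (35.0) | 5-30%, 0.5-2 | 36.7-52.1 | 7.1-12.5 | 29.6-39.6 | 35.1-35.4 |
| HiSCR75 | 10%, 0.8-1.25 | 42.1-46.5 | 8.8-10.3 | 33.3-36.2 | 35.1 |

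With the antibiotic odds ratio at 1 and only Hurley stage acting, D is 35.3 (HiSCR50) and 34.7 (HiSCR75). The assumed Hurley imbalance therefore adds less than 1 point, and the shift comes almost entirely from antibiotic use.

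**Second check, 50% v 25%.** With 10% users, OR 0.5 and no Hurley effect, equal weights give 43.1% v 20.0%, difference 23.1 against 25.0. If neither factor is prognostic, the result is exactly 50.0, 25.0 and 25.0.

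**Standard error.** The variance of the log odds ratio is S_R² = S_B² + S_P² − 2Cov. The last two terms under the printed root therefore equal −2·P_B(1−P_B)·P_P(1−P_P)·Cov. This is the correct delta-method variance for D as defined; a numerical check gave 0.06156 both ways.

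**The case against.** The strongest reply is that equal weighting is not SAP text. It is inferred from a software default, and the enrolled mix is unknown. That stands: a reader might infer that the plan prescribes 50/50 weights, or that the reported rates describe a population the trial did not enrol, and the document supports neither. What can be said is that the weights are not fixed.

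Second, the estimand's summary measure in section 8.2.2 is the conditional odds ratio, and D is introduced as an addition to it. That also stands. A reader might infer that the primary effect or its test is distorted; it is not, because least squares mean weights do not enter the odds ratio, the Wald test or the sequence in section 4.5.

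Third, crude information is planned: unadjusted arm proportions (section 4.2.2.1), counts and percentages of HiSCR50 responders (section 8.2.2), summaries by Hurley stage and antibiotic use (section 8), and subgroup differences with confidence intervals (section 4.8). This limits the harm, but none of it supplies an unadjusted overall difference beside D.

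Fourth, the size is assumed and small beside sampling error. For HiSCR50 the 95% half-width is about 1.96·√(0.6·0.4/280 + 0.25·0.75/70) = 0.117, or 12 points, and the larger HiSCR75 shifts need odds ratios near 0.5 or 2, which nothing in the SAP suggests. That is fair, but the shift is systematic, and no choice of weights removes the averaging problem.

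**Conclusion.** The point holds as a defect in how the supplementary absolute rates and differences are defined. They are inverse logits of mean log odds, with weights left open, yet are labelled as proportions of responders.

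Under equal weights and the assumed ranges (antibiotic share 5-30%, odds ratio 0.5-2, Hurley III 45% with odds ratio 0.6), arm rates move by up to about 8 points, and D by about 2 points for HiSCR50 and up to about 5 for HiSCR75. With antibiotic odds ratios of 0.8-1.25 the shift in D is about 1 point and up to about 2 points respectively. It is zero if neither factor is prognostic. The actual size cannot be known from the SAP.

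The odds ratio, p-values, alpha, testing sequence and unadjusted arm proportions are unaffected, and S_D is right for D as defined. This is a worthwhile low-cost improvement to the descriptive estimates, not a threat to the primary inference.

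**What to change.** Keep the logistic model, the odds ratio and the Wald test. For the adjusted rates and D, replace the least squares mean step in section 4.2.2.1 as follows. In each imputed data set, predict every Randomized Set participant's response probability under the bimekizumab regimen and under placebo, average each over all participants, and take the difference. For skin pain response, average over those with a Baseline score of 3 or higher. Use the delta-method standard error that matches these averages, and pool with Rubin's rules.

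At the least, state that the least squares means use observed margins. In the examples above this brings D to 35.1-36.2 against 35.0; what remains is the averaging on the logit scale.

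The cost is a few lines of SAP wording and a short macro. No test or alpha allocation changes. The printed S_D formula would be replaced only because the quantity it belongs to changes.

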4.2.2.2 MI – MCMC / Reference-based imputation

MI-MCMC / Reference-based imputation will be implemented as a supportive analysis for the primary efficacy endpoint (through Week 16).

In this case, placebo will be described as the reference arm.

This procedure will use an imputation model based on data from the placebo group only (Mallinckrodt, 2013). Reference-based MI assumes that the statistical behavior of the bimekizumab and placebo-treated participants after discontinuing study medication becomes that of the placebo-treated participants. All timepoints after discontinuation of the double-blind study treatment for both the bimekizumab and placebo groups will be considered missing. Multiple imputations are used to replace missing outcomes for bimekizumab- and placebo-treated participants who discontinued using multiple draws from the posterior predictive distribution estimated from the placebo arm. For binary efficacy endpoints (eg, HiSCR₅₀ at Week 16), imputation will be done on the lesion counts before assessing the imputed results for HiSCR₅₀ response.

The steps for the procedure are as follows:

1. For non-monotone (intermittent) missing data, MCMC will be used to impute lesion count data, with Baseline antibiotic use, Hurley Stage at Baseline, and lesion count at Baseline and at each post-Baseline visit (in chronological order) being included in the imputation model. This will be done only once for each participant in order to provide a dataset with monotone missing data.
2. Data will be processed sequentially by repeatedly calling SAS® PROC MI to impute missing outcome data at visits $t=1, \dots, T$, where T is Week 16 for HiSCR₅₀.
 - a. *Initialization.* Set $t=1$ (Baseline visit)
 - b. *Iteration.* Set $t=t+1$. Create a data set combining records from bimekizumab- and placebo-treated participants with columns for covariates (Hurley Stage at Baseline and Baseline antibiotic use) and outcomes at visits 1 to t . Outcomes for all bimekizumab-treated participants are set to missing at visit t and set to observed or previously imputed values at visits 1 to $t-1$. Outcomes for placebo-treated participants are set to observed at visit t or observed or previously imputed values at visits 1 to $t-1$. The outcomes should be sorted in chronological order in the model.
 - c. *Imputation.* Impute missing values for visit t using previous outcomes for visits 1 to $t-1$, Baseline antibiotic use, and Hurley Stage at Baseline. Note that only placebo data will be used to estimate the imputation model since no outcome is available for bimekizumab-treated participants at visit t . Consequently, the input dataset should include all study participants from placebo but only study participants from the bimekizumab arm that have values at timepoint t missing.
 - d. Repeat steps 2a-2c, 100 times with different seed values (seeds ranging from 853 to 952) to create 100 imputed complete data sets. Study participants whose missing values were imputed in the last PROC MI call will be included in the input dataset for the next PROC MI call. Standard rounding rules will be applied to the imputed values. If the MI procedure yields a value outside of the pre-defined range for the given variable, the value will be updated to be within the predefined range of values for the endpoint of interest. For example, the imputed value for inflammatory nodules will be updated to 0 in the case of an imputed value less than 0.
 - e. *Analysis.* For each completed data set, the outcome (response or change from Baseline) will be calculated using the complete datasets (with no missing data).
3. Each complete imputed data set will then be analyzed based on the statistical model specified in this study (logistic regression). The Week 16 results from logistic regression of each of the 100 imputed data sets will be combined for overall inference using Rubin's rules, which account for the uncertainty associated with the imputed values (Rubin, 1987). This will be done using SAS PROC MIANALYZE.

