1. Data after intercurrent event date (See Section 3.9) will be set to missing.
2. The same MCMC method described in Section 4.2.2.1 (Step 1a) will be implemented for non-monotone (intermittent) missing pattern values, using the same imputation model. This will be based on 100 sets of imputations.
3. Based on the 100 datasets obtained in Step 2, a monotone regression model will be applied (using the same imputation model as in Step 2) as described in Section 4.2.2.1 (Step 1b). This will be based on 1 imputation.
4. Delta adjustments will be made to imputed lesion count values at Week 16, independently in each treatment group as described below.
5. Delta adjusted imputed values will be truncated so that they are within the range of allowable values for each component.
6. Following the delta adjustments for the lesion counts, HiSCR₅₀ will then be derived based on the delta-adjusted multiply imputed data sets obtained for each component.
7. Each of the 100 imputed datasets will then be analyzed using a logistic regression model with factors of treatment group, Baseline Hurley Stage, and Baseline antibiotic use.

8. The results obtained from the 100 logistic regression analyses in Step 7 will be combined for overall inference using Rubin's rules, and the results obtained for each shift parameter will be presented in a single table.
9. Steps 4 to 8 will be repeated so that, at each iteration, missing values are adjusted with a larger delta than at the previous iteration. The process will go on until the p-value for the odds ratio between bimekizumab and placebo is no longer statistically significant (eg, ≥ 0.025). The odds ratio, 97.5% CI (or 95% depending on the significance level being used for testing), and p-values obtained for each value of delta will be combined in one single table.

The delta adjustments result in study participants randomized to bimekizumab with missing data having a lower probability of response compared to study participants randomized to placebo with missing data. Since HiSCR₅₀ response is an endpoint for which high lesion counts are associated with a less favorable outcome:

- A positive adjustment is applied to the imputed value for study participants randomized to bimekizumab in order to increase the imputed value and decrease the likelihood of response.

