8.2 Primary efficacy endpoint

The primary and sensitivity analyses of HiSCR₅₀ response at Week 16 are summarized in Table 8–1.

Table 8–1: Estimand Details and Attributes for Primary Endpoint

Objective Clinical Category	Statistical Category (Section)	Estimands for Primary Endpoint			PLS (Analysis)
		Variable/Endpoint	Pop	IES	
Primary Objective: To evaluate the efficacy of bimekizumab in study participants with moderate to severe HS					
HiSCR ₅₀	Primary (Section 8.2.2)	HiSCR ₅₀ response at Week 16	RS	The main intercurrent events are receipt of systemic antibiotic rescue medication or discontinuation of study treatment due to an AE or lack of efficacy prior to Week 16. A composite strategy will be used, ie, the occurrence of an intercurrent event will be handled by evaluating the corresponding participants as treatment failures (nonresponders).	The odds ratio versus placebo based on a logistic regression. Missing values will be imputed using MI – MCMC/Monotone Regression under a missing at random assumption.

Table 8–1: Estimand Details and Attributes for Primary Endpoint

Objective Clinical Category	Statistical Category (Section)	Estimands for Primary Endpoint			PLS (Analysis)
		Variable/Endpoint	Pop	IES	
HiSCR ₅₀	Sensitivity (Section 8.2.3.1)	HiSCR ₅₀ response at Week 16	RS	Composite strategy , as for the primary analysis where the occurrence of an intercurrent event will be handled by evaluating the corresponding participants as nonresponders.	The odds ratio versus placebo based on a logistic regression. Missing values for any other reason will also be imputed as nonresponders.
HiSCR ₅₀	Sensitivity (Section 8.2.3.2)	HiSCR ₅₀ response at Week 16	RS	Composite strategy , as for the primary analysis.	The odds ratio versus placebo based on a logistic regression. Missing values will be imputed using MI – Reference-Based Regression under a missing not at random assumption.

Table 8–1: Estimand Details and Attributes for Primary Endpoint

Objective Clinical Category	Statistical Category (Section)	Estimands for Primary Endpoint			PLS (Analysis)
		Variable/Endpoint	Pop	IES	

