8.2.3.2 MI-MCMC / Reference-based imputation

Deviations from the missing at random pattern will be evaluated using a reference-based MI approach (see Section 4.2.2.2). Intermittent missing data will be imputed using the MCMC method. The remaining monotone missing data will be assumed to follow a missing not at random pattern. These data will be imputed using a reference-based approach in which the MI model is based on data from the placebo group, thereby assuming that monotone missing data follow a trajectory similar to the placebo group.

The same analysis model as in the primary efficacy analyses will then be used on the imputed data set.

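### SAP 4.2.2.2 discards Week 16 counts that the primary analysis keeps, against the Table 8–1 row for the reference-based sensitivity analysis, and fills intermittent gaps only once

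*SAP*

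**What the plan says.** SAP 4.2.2.2 assumes that participants in all arms behave like placebo participants once they stop study medication. It then sets a data rule: "All timepoints after discontinuation of the double-blind study treatment for both the bimekizumab and placebo groups will be considered missing". The rule makes no distinction by reason for stopping. The removed values are replaced "using multiple draws from the posterior predictive distribution estimated from the placebo arm".

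Table 8–1 describes the same analysis in its row for Section 8.2.3.2. The intercurrent event strategy is "Composite strategy , as for the primary analysis", and the analysis column says: "Missing values will be imputed using MI – Reference-Based Regression under a missing not at random assumption". The text of 8.2.3.2 agrees with the table. After the MCMC fill of intermittent gaps, it says: "The remaining monotone missing data will be assumed to follow a missing not at random pattern". Neither place mentions removing observed data.

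For the primary analysis, Section 3.9 limits intercurrent events to systemic antibiotic rescue and to discontinuation for an AE or lack of efficacy. Section 8.2.2 adds: "Any missing data at Week 16 that are not preceded by an intercurrent event will be imputed using multiple imputation".

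On the mechanics, Step 1 of 4.2.2.2 says of the MCMC fill: "This will be done only once for each participant in order to provide a dataset with monotone missing data". Step 2d then repeats only Steps 2a to 2c, 100 times. The tipping-point procedure in 4.2.2.3 says of the same MCMC step: "This will be based on 100 sets of imputations".

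**The concern.** Section 8.2.3 says that its analyses test the missing-data assumptions behind the primary result. That works only if the reference-based analysis changes the imputation and leaves observed data alone. The rule in 4.2.2.2 does more. A participant who withdraws from treatment for, say, a personal reason, but attends Week 16, has a real off-treatment lesion count. That count is direct evidence of what happens after stopping, and it is replaced by a model draw. Such counts are expected: 4.2.1.4 describes participants who stop treatment and keep attending visits, and 8.2.3.4 says efforts will be made to obtain Week 16 data from everyone.

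Two things are at stake. Two programmers, one following Table 8–1 and the other 4.2.2.2, could obtain different results for a pre-specified sensitivity analysis of the primary endpoint. And a gap between this result and the primary one could not be attributed to the missing-not-at-random assumption alone.

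**Working it through.** **Which participants are affected.** Setting the sections side by side:

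| Participant | Primary (3.9, 4.2.1.1, 8.2.2) | Table 8–1 and 8.2.3.2 | 4.2.2.2 |
|---|---|---|---|
| Antibiotic rescue, or stops for AE or lack of efficacy | Nonresponder | Nonresponder | Left to Table 8–1 by the opening of 4.2.2: nonresponder |
| Stops for another reason, no rescue, Week 16 missing | Imputed under MAR | Placebo model | Placebo model |
| Stops for another reason, no rescue, Week 16 observed | Observed count | Observed count | Count deleted, placebo model |

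Only the last row conflicts. The opening remark of 4.2.2 does not resolve it, because it defers the handling of intercurrent events, and stopping for another reason is not one under 3.9. No other section cancels the deletion. The neighbouring tipping-point procedure sets data to missing only after the intercurrent event date.

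**Planning figures.** Inputs from 2.4 and Table 2–1: bimekizumab arm n = 140, rate 0.50; placebo n = 70, rate 0.25; two-sided alpha 0.025. The plan's own power can be reproduced with the normal approximation:
- pooled rate = (140 × 0.50 + 70 × 0.25)/210 = 0.4167
- null SE = sqrt(0.4167 × 0.5833 × (1/140 + 1/70)) = 0.0722
- alternative SE = sqrt(0.25/140 + 0.1875/70) = 0.0668
- power = Φ((0.25 − 2.2414 × 0.0722)/0.0668) = 0.907, against a stated 0.90

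**Size of the deletion.** Let f be the share of the arm in the conflicting row, q their observed response rate, and 0.25 the approximate rate of the placebo-model draws. The shift in the arm rate is f × (0.25 − q). The SAP does not give f, so 1% to 10% is assumed (1.4 to 14 of 140). The placebo rate is held at 0.25 (odds 1/3), and the odds ratio without the deletion is 3.00.

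| f | q | Shift (points) | New rate | Odds ratio |
|---|---|---|---|---|
| 1% | 0.50 | −0.25 | 0.4975 | 2.97 |
| 10% | 0.50 | −2.5 | 0.475 | 2.71 |
| 1% | 0 | +0.25 | 0.5025 | 3.03 |
| 10% | 0 | +2.5 | 0.525 | 3.32 |

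The sign depends on how these participants actually responded. If they kept the arm's response rate, the draws lower the estimate. If none responded, the draws raise it.

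**Step 1.** Rubin's total variance is W + (1 + 1/M)B, where W is the average within-data-set variance, B the variance between data sets, and M = 100. With one Step 1 fill shared by all 100 data sets, B reflects only the later placebo-model draws and contains nothing from the intermittent fill. Section 4.2.2.2 runs through Week 16 and sets T to Week 16, so a missing Week 16 value has no later visit, is monotone, and is not filled by Step 1. The fixed fill therefore enters only through earlier visits used as predictors.

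**The case against.** The strongest case on the other side has four parts.

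- *The rule follows from the stated assumption.* If behaviour after stopping is taken to be that of placebo, treating later data as missing is coherent. That is so, but it describes a different strategy for discontinuation, and Table 8–1 does not declare one.
- *The off-treatment evidence is used elsewhere.* The treatment policy analysis in 8.2.3.4 uses all Week 16 data whatever the reason for stopping. This stands and limits the harm. It does not reconcile 4.2.2.2 with Table 8–1.
- *The primary's use of these counts is inferred.* Section 8.2.2 also speaks of completing study treatment through Week 16. But its intercurrent event attribute and 3.9 name only rescue and AE or lack-of-efficacy discontinuation, and 4.2.1.1 imputes only what remains missing. The inference is sound.
- *The sizes are rough.* This stands. Step 2c conditions on each participant's earlier counts, so a flat 0.25 is an approximation.

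A reader might also infer that participants who stop for an AE or lack of efficacy regain a chance of response here, because Steps 2e and 3 contain no reset to nonresponse. The SAP does not support that. The opening of 4.2.2 sends intercurrent events to the analysis sections, Table 8–1 makes these participants nonresponders, and the only stated exception is for the tipping-point analysis (4.2.2.3 and footnote a of Table 8–1).

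**Conclusion.** The conflict is real and narrow. It concerns other-reason discontinuers without rescue who have Week 16 counts, in the placebo arm as well as the bimekizumab arms. For them 4.2.2.2 contradicts Table 8–1 and 8.2.3.2, and the analysis changes more than the missing-data assumption. On an assumed 1% to 10% of a 140-participant arm, the shift is roughly 0.25 to 2.5 points in either direction. This rests on Table 2–1 rates, draws at about 0.25, an observed rate among those affected between 0 and 0.50, and an unchanged placebo rate. It is an illustration, not a bound.

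The single fill in Step 1 is a separate and probably small defect. A reader might suppose that it leaves the Week 16 response rate resting on one random draw. With the procedure ending at Week 16 that does not follow.

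The primary estimate and the multiplicity procedure are untouched, and nonresponse, tipping-point and treatment policy analyses run alongside. This is a minor correction.

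**What to change.** In 4.2.2.2, remove the deletion rule. State that only values actually missing are drawn from the placebo model, and that Week 16 counts observed after discontinuation for other reasons are kept. If the deletion is intended, keep it and declare that different strategy in the Table 8–1 row for 8.2.3.2 and in the text of 8.2.3.2.

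In Step 1, generate 100 MCMC fills and run one reference-based draw on each, following the structure of Steps 2 and 3 in 4.2.2.3.

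The cost is SAP wording and a small program change. No new data are needed.
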